10.2 Secondary Efficacy Variables

The secondary efficacy variables are:

- Percentage of time spent in AF (AF Burden) during the first 30 days post-surgery
- Percentage of participants with at least 1 event of symptomatic AF (symptoms occurring within 2 hours of an AF episode) during the first 30 days post-surgery
- Time to first occurrence of AF during the first 30 days post-surgery
- Percentage of participants with at least 1 continuous AF episode ≥ 2 minutes during the first 30 days post-surgery
- Percentage of participants with at least 1 continuous AF episode ≥ 5 minutes during the first 30 days post-surgery
- Percentage of participants with at least 1 continuous AF episode ≥ 6 minutes during the first 30 days post-surgery
- Percentage of participants with at least 1 continuous AF episode ≥ 30 minutes during the first 30 days post-surgery
- Percentage of participants with at least 1 continuous AF episode ≥ 1 hour during the first 30 days post-surgery
- Percentage of participants with at least 1 continuous AF episode ≥ 4 hours during the first 30 days post-surgery
- Percentage of participants with at least 1 continuous AF episode ≥ 6 hours during the first 30 days post-surgery
- Percentage of participants with at least 1 continuous AF episode ≥ 12 hours during the first 30 days post-surgery
- Percentage of participants with at least 1 continuous AF episode ≥ 24 hours during the first 30 days post-surgery
- Percentage of participants with at least 1 continuous atrial fibrillation (excluding atrial flutter) episode ≥ 30 seconds during the first 30 days post-surgery
- Percentage of participants with at least 1 continuous atrial flutter episode ≥ 30 seconds during the first 30 days post-surgery

- Percentage of participants with at least 1 continuous atrial tachycardia episode (defined as the duration of the longest SVT run) \geq 30 seconds during the first 30 days post-surgery
- Percentage of participants with at least 1 continuous episode of either atrial fibrillation or atrial flutter or atrial tachycardia \geq 30 seconds during the first 30 days post-surgery

Between-group treatment comparisons in the percentage of time spent in AF (AF burden) during the first 30 days post-surgery will be performed for each AGN-151607 treatment arm versus placebo using the stratified Wilcoxon (Van Elteren) test stratified by age group and type of surgery. Calculation of time spent in AF (AF burden) will exclude continuous AF episodes < 30 seconds in duration. For participants with no AF during the first 30 days post-surgery, the AF burden will be set to 0.

For each efficacy variable with binary categorical response outcome, the response proportions will be analyzed using the same methods used to analyze the primary efficacy variable. For symptomatic AF, symptoms that occur in the interval that starts two hours prior the onset of the AF episode and ends two hours after the conclusion of the AF episode will meet the definition of "within 2 hours of an AF episode". As noted in the protocol, participants will mark the date and time that a symptom is experienced by pressing a button on the ECG patch itself.

For each treatment group, the Kaplan-Meier (KM) survival analysis methodology will be used to estimate the median time (days) to first occurrence of AF during the first 30 days post-surgery using each of the 9 definitions of POAF stated in Section 10.0 above. Furthermore, the 25th and 75th percentiles of the time to the first occurrence of AF during the first 30 days post-surgery will also be estimated. The associated 95% CIs calculated using Greenwood's formula for the variance of the KM estimate will also be presented for each treatment group. Pairwise treatment comparisons of the KM curves will be performed primarily by using the log rank test stratified by type of surgery and age group. Time to event data will also be compared between treatment groups using Cox proportional hazards models adjusting for baseline risk factors of POAF (type of surgery, and age group), with hazard ratios and their 95% CIs presented for each pairwise comparison. Cox proportional hazards models additionally adjusting for total analyzable time during the first 30 days post-surgery will also be analyzed. The difference in restricted mean survival time between treatment groups for time to first occurrence of AF during the first 30 days post-surgery (i.e., restricted time $\tau = 30$ days) will be compared using a nonparametric K-sample chi-square test stratified by type of surgery and age group. Participants who do not experience an AF episode during the first 30 days post-surgery will be censored at the maximum timepoint during the first 30 days post-surgery for which they have recorded data.

For the time to first occurrence of AF during the first 30 days post-surgery, a supplementary analysis will be performed based on the Supplementary ePatch Analysis Sets (SEA-7 and SEA-30). The supplementary analysis will use the same methods described above.

For each minimum duration specified above for the percentage of participants with at least 1 continuous AF episode during the first 30 days post-surgery, a supplementary analysis will be performed based on the Supplementary ePatch Analysis Sets (SEA-7 and SEA-30). The supplementary analysis will use the same methods used to analyze the primary efficacy variable. For these endpoints, subgroup analyses will also be performed using the same methods described above based on the correct stratification group [type of surgery (presence or absence of valve surgery) and age group (< 65 or \geq 65 years)].

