#### 8.1.3.2. Symptomatic Post-operative Atrial Fibrillation

The occurrence of POAF is often associated with the onset of particular symptoms, such as dizziness, palpitations, and fatigue. All participants will be wearing ECG patches with the ability to mark the date and time that a symptom is experienced by simply pressing a button on the ECG patch itself (Table 8-3). While the participant is wearing the ECG patch, if symptoms of AF occur, the actual symptom will be documented by the participant in a symptom diary. Participants will be instructed by the site staff or designee on the appropriate completion of the symptom diary and instructions will be included with each diary.

Table 8-3	Assessment of Symptomatic Post-operative At	rial Fibrillation
	Assessment of Symptomatic 1 0st-operative At	i lai i ini mation

Assessment	Timing		Measurement
Occurrence of symptomatic POAF	Through Day 30 and for 7 days after each of the following study visits: Day 60, Day 90, Day 180, Say 270, and Day 360	•	Participants will press their ECG patch when they experience a symptom and then log the symptom in a diary. The information will be used to identify cases of symptomatic POAF.

AF = atrial fibrillation; ECG = electrocardiogram; POAF = post-operative atrial fibrillation

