- Percentage of participants with at least 1 event of symptomatic AF (symptoms occurring within 2 hours of an AF episode) during the first 7 days following Day 60, Day 90, Day 180, Day 270, and Day 360 visits
- Percentage of participants with actionable AF within 30 days post-surgery. Actionable AF is defined as meeting at least one of the following conditions: hospitalization due to AF, or medicinal or procedural intervention due to AF
- Percentage of participants discharged from hospital (after initial care of indication under study) without prescription of any of the medication of interest listed in Section 8.0
- Percentage of participants free from AF through 12 months post-surgery and not taking any antiarrhythmic drugs (as defined in Section 8.0)
- Percentage of participants free from AF through 12 months post-surgery and not taking any anticoagulant drugs (as defined in Section 8.0)
- Percentage of time spent in AF (AF burden) during the first 7 days following Day 60, Day 90, Day 180, Day 270, and Day 360 visits

The first 6 variables above will be analyzed using the same method used to analyze the primary efficacy variable in Section 10.1. Similarly, the AF burden will be analyzed using the same method discussed in Section 10.2. In addition, descriptive statistics of the AF Burden, including tertiles, will be presented by treatment group. For symptomatic AF, symptoms that occur in the interval that starts two hours prior the onset of the AF episode and ends two hours after the conclusion of the AF episode will meet the definition of "within 2 hours of an AF episode". The date and time when a symptom is experienced is marked by a participant pressing a button on the ePatch itself.

Page 22

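### The symptomatic-AF rule accepts symptoms up to 2 hours either side of an AF episode, sets no minimum episode length and is silent on the diary, so unrelated symptoms can be counted

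*SAP*

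**What the plan says.** SAP 10.2 lists the secondary variable as "Percentage of participants with at least 1 event of symptomatic AF (symptoms occurring within 2 hours of an AF episode) during the first 30 days" after surgery. The operative sentence then counts "symptoms that occur in the interval that starts two hours prior the onset of the AF episode and ends two hours after the conclusion" (when that episode ends). SAP 10.3 applies the same interval to the 7-day recordings after the Day 60 to Day 360 visits. Neither section gives a reason for two hours.

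**Timing of the symptom.** SAP 10.2: "participants will mark the date and time that a symptom is experienced by pressing a button on the ECG patch itself". SAP 10.3: "The date and time when a symptom is experienced is marked by a participant pressing a button on the ePatch itself".

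**Episode length.** SAP 10.0 defines an AF episode by rhythm (fibrillation or flutter), with no duration. A 30-second minimum is written for the primary endpoint (10.1), for AF burden (10.2) and for the count of AF events (10.3). None is written for symptomatic AF.

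**Diary.** Protocol 8.1.3.2 says "the actual symptom will be documented by the participant in a symptom diary". Its Table 8-3 says "Participants will press their ECG patch when they experience a symptom and then log the symptom in a diary", and then "The information will be used to identify cases of symptomatic POAF". The footnotes to SAP Table 4-1 keep the diary, and SAP 16 lists no change that removes it. The SAP rule itself does not mention it.

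**The concern.** The endpoint is meant to capture AF that patients feel. Three features of the rule loosen that link.

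- **Window.** It credits symptoms felt before AF was recorded, and symptoms well after it ended. Press and ECG come from the same patch, and SAP 15.8 reports that relative time within a patch is accurate even after a clock reset. Clock error between press and ECG therefore does not explain two hours.
- **Episode length.** Read literally, a run of a few seconds opens a window of just over four hours, and a participant could have symptomatic AF without POAF by the primary definition.
- **Diary.** The protocol uses press and diary together to identify cases. The SAP does not say whether a press without a diary entry counts, so two programmers could derive different results.

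Protocol 8.1.3.2 gives dizziness, palpitations and fatigue as example symptoms. These are not specific to AF after cardiac surgery. Only participants with recorded AF can be miscounted, so false counts follow AF incidence. A treatment difference on this endpoint could then partly repeat the AF-occurrence result.

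**Working it through.** The documents give no rate, press count or episode count for symptomatic AF, so there is no planned figure to reproduce on this point, and power for the endpoint cannot be computed. What follows is an illustration under assumptions.

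**Inputs**
- From the SAP: 2 hours each side of the episode, and 30 days = 720 h of monitoring.
- Assumed: k episodes of length L hours with non-overlapping windows; m presses unrelated to AF; presses spread evenly; complete recording.

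**1. Window against episode.** A 30-second episode opens 4 h 30 s = 14,430 s, and 14,430/30 = 481 times its own length.

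**2. Chance of at least one false count**, given AF: 1 − (1 − k(L + 4)/720)^m, with L = 30 s = 0.00833 h.

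| Episodes k | Share of time covered | m = 5 | m = 10 |
|---|---|---|---|
| 1 | 4.0083/720 = 0.56% | 2.8% | 5.4% |
| 5 | 20.042/720 = 2.78% | 13.2% | 24.6% |
| 10 | 40.083/720 = 5.57% | 24.9% | 43.6% |

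Ten 1-hour episodes with 5 presses: share 50/720 = 6.94%, chance 30.2%.

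**3. The two hours before onset alone**, m = 5: 1 − (1 − 2k/720)^5 gives 1.4% (k = 1), 6.8% (k = 5) and 13.1% (k = 10), about half of the total.

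**4. Symptoms inside the episode only**, m = 5: 1 − (1 − kL/720)^5. Ten 30-second episodes give 0.06%. Ten 1-hour episodes give 1 − (1 − 10/720)^5 = 6.8%, so a stricter rule reduces false counts but does not remove them when episodes are long.

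**5. Clustering in week 1.** Assume 70% of episodes and presses fall in the first 168 h, with 1-minute episodes (window 4.017 h). For one episode and 5 presses:
- Episode in week 1: chance per press 0.7 × 4.017/168 = 0.0167; over 5 presses 8.1%.
- Episode later: 0.3 × 4.017/552 = 0.0022; over 5 presses 1.1%.
- Combined: 0.7 × 8.1% + 0.3 × 1.1% = 6.0%.

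A simulation with the same clustering (40,000 participants per scenario, overlap allowed) gives 16.9% for 3 episodes and 5 presses, and 45.5% for 10 and 5. With even spread it gives 8.1% and 24.2%.

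**6. Arm level.** Take the planned incidences of 47.8% and 27.8%, a 30-second floor, equal episode and press counts among those with AF, and no true symptoms. False counts then create a difference of chance × 20 points: 0.028 × 20 = 0.6, 0.132 × 20 = 2.6 and 0.249 × 20 = 5.0 points for 1, 5 and 10 episodes. True symptomatic cases would leave fewer participants to miscount, so for given counts these are ceilings.

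**The case against.** Several stronger readings are tempting, and the documents do not support them.

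- **The diary has been dropped and any press counts.** A reader might infer this from the SAP's silence. But the SAP speaks of symptoms, refers back to the protocol for the press, keeps the diary in its schedule and lists no change that removes it. The gap is an unstated requirement.
- **A symptom before onset cannot belong to the episode.** Onset is the onset seen in analyzable patch data. SAP 10.0 imputes nothing for gaps, and SAP 6.3 provides for substantial missing data. True onset can precede recorded onset. That defeats an absolute claim but does not justify a full two hours.
- **Symptomatic AF without POAF is intended.** Protocol 8.1.3.2 calls the outcome symptomatic POAF, and every listed POAF definition starts at 30 seconds or longer. A floor can be inferred, but it is written elsewhere in the SAP and not here.
- **The endpoint cannot show a symptom effect, or participants are often misclassified.** True symptomatic episodes still count. Any symptomatic-AF endpoint follows AF incidence to some degree, because AF is a precondition. With one episode and few presses the false share is small, and 5 to 10 unrelated presses is not established.
- **The SAP contradicts a 30-minute window.** That window appears only as deleted text in the amendment summary, and nothing here rests on it.

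The stakes are also limited. This is one of 16 secondary variables in a Phase 2 trial, without multiplicity control beyond the primary endpoint, and blinding makes unequal reporting of unrelated symptoms between arms unlikely. What stands is a wide window with no stated reason, a missing minimum length and an undefined role for the diary.

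**Conclusion.** The concern holds as a matter of definition. Followed as written, the rule can count unrelated symptoms in participants with AF, including those before recorded onset or near runs under 30 seconds, and it pulls the endpoint toward AF incidence. With 5 unrelated presses the chance of a false count, given AF, is about 3% with 1 episode, 13% with 5 and 25% with 10. Clustering in week 1 raises the first to about 6% and the last to about 45%. These figures rest on assumed counts, on presses independent of AF and on complete recording. They show when the rule matters and do not estimate what happened in the trial. The primary endpoint is unaffected.

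**What to change.** In SAP 10.2 and 10.3:

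1. Limit qualifying episodes to continuous AF of at least 30 seconds, in line with the primary POAF definition.
2. State whether a press needs a matching diary symptom, consistent with protocol Table 8-3.
3. Add a prespecified analysis that counts only symptoms marked between onset and end of a qualifying episode, and report it beside the 2-hour rule. A short tolerance each side is optional; the documents offer no basis for a particular length.

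The cost is SAP wording and one extra derivation, with no new data collection. The symptomatic-AF rate will be lower, and the stricter analysis may miss some true symptoms near gaps in the recording. Reporting both analyses keeps those symptoms visible.

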10.3 Additional Efficacy Variables

Hospital and ICU Length of Stay

Hospital length of stay for the initial care of indication under study is defined as the time (days) from ICU admission date/time to the date/time of discharge from the hospital. ICU length of stay is defined as the time (hours) from the ICU admission date/time to the date/time of discharge from the ICU. For participants not admitted to the ICU, ICU length of stay will be set to zero and hospital length of stay will be defined as the time (days) from end date/time of study drug administration to date/time of discharge from hospital. For subjects missing ICU admission date/time, ICU admission date/time will be imputed to the end date/time of study drug administration. The date/time of death will be used to derive hospital length of stay for participants who died at the hospital (and ICU length of stay, for participants who die in the ICU).

Descriptive statistics (n, mean, SD, Q1, median, Q3, min, max) for hospital and ICU length of stay will be presented by:

- treatment group
- region (U.S. versus non-U.S.) and treatment group
- country and treatment group
- sites and treatment group

Between-group treatment comparisons in hospital and ICU length of stay will be performed for each AGN-151607 treatment arm versus placebo using the following methods:

- An ANOVA model with treatment group, type of surgery, age group, and region as factors
- An ANOVA model with treatment group and region as factors
- An ANOVA model with treatment group and country as factors

- A stratified Wilcoxon (Van Elteren) test, stratified by type of surgery, age group, and region
- A stratified Wilcoxon (Van Elteren) test, stratified by type of surgery and age group

Descriptive statistics of hospital length of stay measured from the time of initial hospital admission to discharge will be presented by:

- treatment group
- region (U.S. versus non-U.S.) and treatment group
- country and treatment group
- sites and treatment group

ANOVA models, as described above, will be used to estimate confidence intervals for difference in mean hospital length of stay measured from the time of initial hospital admission between each AGN-151607 treatment arm and placebo.

Descriptive statistics of number of days spent in the hospital within 30 days post-discharge and within 60 days post-surgery will be presented by treatment group. Summary statistics will also be presented by treatment group for the reasons for hospital and ICU admissions.

Rehospitalization within 30 Days Post-Discharge and 60 Days Post-Surgery

The percentage of participants with at least one all-cause rehospitalization within 30 days postdischarge and percentage of participants with at least one all-cause rehospitalization 60 days post-surgery will each be presented by treatment group. Similar summaries will be presented for non-arrhythmia cardiovascular rehospitalization and arrhythmia cardiovascular rehospitalization. These variables will be analyzed using the same method presented for the primary efficacy variable in Section 10.1. Descriptive statistics of the total number of rehospitalizations within 30 days post-discharge and 60 days post-surgery as well as the length of rehospitalization stay will also be presented by treatment group for each of the different causes of rehospitalizations (allcause, non-arrhythmia cardiovascular and arrhythmia cardiovascular).

The time (days) to the first all-cause rehospitalization will be calculated as the date/time of first re-hospitalization minus the date/time of hospital discharge after surgery. This will be analyzed using the KM method discussed in Section 10.2. Participants with no rehospitalizations will be censored at their respective study exit day. Similar analyses will be performed for non-arrhythmia cardiovascular rehospitalization and arrhythmia rehospitalizations.

Healthcare Resource Utilization within 30 Days, 60 Days, and 365 days Post-Discharge

The proportion of participants with any healthcare resource utilization (outside of any planned in-patient hospitalization, procedures and medications) within 30 days, 60 days, and 365 days post-discharge will be presented by treatment group. The type of resource utilized (e.g., Outpatient hospital, Physician's office, etc.) as well as the reason for the visit will also be tabulated in a similar manner. Descriptive statistics of the number of times each participant utilizes a healthcare resource within each of the specified timeframe will also be presented by treatment group. Note that any unplanned inpatient hospitalization will also be included in these summaries.

Need for Medical or Procedural Intervention Due to AF

The following five binary (yes/no) variables will be used to analyze the need for pharmacologic and/or procedural intervention due to AF during the first 30 days post-surgery:

- 1. at least one pharmacologic intervention (i.e., anticoagulation or antiarrhythmic drugs)?
- 2. at least one anticoagulation pharmacologic intervention?
- 3. at least one antiarrhythmic pharmacologic intervention?
- 4. at least one procedural intervention (see list in Section 8.0)?
- 5. at least one pharmacologic or procedural intervention?

In addition, time to event variables will also be created for each of the corresponding 5 variables above. The time to the first event will be used for analysis. All these variables will be analyzed using the same methods for similar variables in Sections 10.1 and 10.2.

The need for pharmacologic and/or procedural intervention due to AF from Day 31 to Day 360 post-surgery will be analyzed in a similar fashion. Participants with no events who exit the study prior to Day 360 will be censored at their respective study exit day minus 30 days, while participants with no events who exit the study on or beyond day 360 will be censored at day 330 (360 - 30 = 330). Pharmacologic and/or procedural interventions due to AF with onset dates prior to day 31 that are ongoing at day 31 will count as events for these endpoints, with a time-to-event equal to zero.

Descriptive statistics will be presented by treatment group for each of the following:

- time to POAF resolution from first dose of prescription of pharmacologic intervention
- time to POAF resolution from first procedural intervention
- types of pharmacologic interventions used due to POAF

- will be further categorized by "medication of interest" (antiarrhythmics versus anticoagulants) as defined in Section 8.0 above.
- yes/no: Beta blocking agent (ATC code: C07A) withdrawn within 3 days post-surgery and no replacement (no new beta blocker prescription) within 7 days post-surgery

Other Efficacy Variables

- Percentage of participants with clinically important tachycardia in AF (defined as heart rate ≥ 100 bpm for at least 2 minutes) within 30 days post-surgery
- Percentage of participants with any occurrence of AF as defined in the primary and secondary endpoints during the first 7 days following Day 60, Day 90, Day 180, Day 270, and Day 360 visits
- Percentage of participants with at least 1 event of symptomatic AF (symptoms occurring within 2 hours of an AF episode) during the first 7 days following Day 60, Day 90, Day 180, Day 270, and Day 360 visits
- Percentage of participants with actionable AF within 30 days post-surgery. Actionable AF is defined as meeting at least one of the following conditions: hospitalization due to AF, or medicinal or procedural intervention due to AF
- Percentage of participants discharged from hospital (after initial care of indication under study) without prescription of any of the medication of interest listed in Section 8.0
- Percentage of participants free from AF through 12 months post-surgery and not taking any antiarrhythmic drugs (as defined in Section 8.0)
- Percentage of participants free from AF through 12 months post-surgery and not taking any anticoagulant drugs (as defined in Section 8.0)
- Percentage of time spent in AF (AF burden) during the first 7 days following Day 60, Day 90, Day 180, Day 270, and Day 360 visits

The first 6 variables above will be analyzed using the same method used to analyze the primary efficacy variable in Section 10.1. Similarly, the AF burden will be analyzed using the same method discussed in Section 10.2. In addition, descriptive statistics of the AF Burden, including tertiles, will be presented by treatment group. For symptomatic AF, symptoms that occur in the interval that starts two hours prior the onset of the AF episode and ends two hours after the conclusion of the AF episode will meet the definition of "within 2 hours of an AF episode". The date and time when a symptom is experienced is marked by a participant pressing a button on the ePatch itself.

Page 22

- A negative binomial (NB) regression model will be used to model the number of AF events (using \geq 30 seconds definition of AF) within 30 days post-surgery, with treatment, type of surgery, and age group as factors and log(total analyzable time) as the offset in the model. A zero-inflated negative binomial (ZINB) regression model will also be estimated with treatment, type of surgery, and age group as factors in both the main and zero-count models and log(total analyzable time) as the offset. If p < 0.05 for the Scaled Pearson chi-square goodness of fit statistic for the NB model (suggesting overdispersion may be present), then the ZINB model will be considered the primary analysis; otherwise, the NB model will be considered the primary analysis. Sensitivity analyses of the number of AF events using Poisson regression and zero-inflated Poisson regression using similar models will be performed. Least squares (LS) mean differences and incidence rate ratios with 95% CIs will also be performed based on the SEA-30 set using the same models.
- The win ratio unmatched approach (Pocock et. al., 2012) will be used to analyze the following composite endpoint:
 - 1. Death
 - 2. Stroke
 - 3. All-cause 30-day rehospitalization
 - 4. Use of pharmacologic or procedural intervention of interest due to AF
 - 5. Hospital length of stay

The components of the endpoints are listed in order of clinical importance. The win ratio, with the associated 95% CI and p-value will be presented for the composite endpoint, as well as for each of the component endpoints. Two win ratios analyses will be performed. The first will analyze binary outcomes for each of the components (with the fifth component being "Hospital length of stay > median hospital length of stay for the total study population"). The second will analyze time-to-event outcomes for each of the components (with the time-to-first-event used for components with multiple events experienced, and with the fifth component being time-to-hospital-discharge from initial care). A list of Medical Dictionary for Regulatory Activities (MedDRA) preferred terms for stroke will be provided by the clinical team. All-cause 30-day rehospitalization includes any hospitalization within 30 days of (first) discharge from the hospitalization for initial care.

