#### **Study Rationale**:

Post-operative atrial fibrillation (POAF) occurs at high rates despite standard-of-care therapies and is associated with problematic outcomes, eg, medical/procedural interventions, extended length of stay in the intensive care unit (ICU) and hospital, and rehospitalization. Nonclinical studies have demonstrated that injections of botulinum toxin type A into discrete regions of the heart can prevent atrial fibrillation (AF) and 2 clinical studies have demonstrated that botulinum toxin type A injections can prevent POAF with no noted safety issues.

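### Hospital and ICU length of stay end at death, so an early in-hospital death is compared between arms as a short, favourable stay

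*SAP*

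**What the plan says.** SAP section 10.3 measures hospital stay in days from ICU admission to hospital discharge, and ICU stay in hours from ICU admission to ICU discharge. For deaths it says: "The date/time of death will be used to derive hospital length of stay for participants who died at the hospital". A parenthesis applies the same rule to the ICU stay when the death occurs there.

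Each dose is then compared with placebo in three ANOVA models, the fullest being "An ANOVA model with treatment group, type of surgery, age group, and region as factors", and in two rank tests, one of which is "A stratified Wilcoxon (Van Elteren) test, stratified by type of surgery and age group". The other rank test adds region. For these comparisons the section gives no worst rank, no competing-event method and no sensitivity analysis for death.

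The plan treats shorter as better. The protocol synopsis lists "extended length of stay in the intensive care unit (ICU) and hospital" among the problematic outcomes of post-operative AF. In the binary win ratio the adverse component is "Hospital length of stay > median hospital length of stay for the total study population". Death is placed above stay only in that win-ratio composite, of which the SAP says "The components of the endpoints are listed in order of clinical importance". The same section also plans descriptive statistics for the "number of days spent in the hospital within 30 days post-discharge and within 60 days post-surgery".

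**The concern.** A participant who dies on Day 2 receives a two-day stay, the same value as a participant who goes home well on Day 2. In both the ANOVA and the rank tests, the worst outcome is therefore given one of the best values. If one arm has more early deaths, its stay looks shorter for that reason alone, and a nominal p-value could be read as a benefit in resource use. The protocol's clinical hypotheses (section 4.1.1) include a favourable effect on the use of health care resources. Section 2.3 says that the adverse event profile of the product is not yet fully characterised in humans, so a difference in early deaths cannot be assumed away.

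**Working it through.** The documents give no expected length of stay, no expected mortality and no power for this endpoint, so there is no plan figure to reproduce. The size can only be illustrated.

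**Inputs**
- From the documents: 330 randomised 1:1:1, so 330/3 = 110 per arm; the stay ends at death.
- Assumed: survivors' stay is log-normal with median 7 days and log-SD 0.45; treatment has no effect on survivors' stay; *k* excess deaths occur in one arm, uniformly between 0.5 and 3 days (mean 1.75 days).

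**Mean stay**
- Survivor mean = 7 × exp(0.45²/2) = 7.75 days. SD = 7.75 × √(exp(0.45²) − 1) = 3.67 days.
- Standard error of a difference in means = 3.67 × √(2/110) = 0.49 day.
- Shift in the arm's mean = *k* × (1.75 − 7.75)/110 = −0.0545 × *k* day (unrounded survivor mean).

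**Probability that a participant in this arm has the shorter stay**
- Let *d* = *k*/110, and let *q* be the chance that a survivor's stay is shorter than a death time. Averaged over 0.5 to 3 days, *q* = 0.005.
- Under the SAP rule: 0.5(1 − *d*) + *d*(1 − *q*).
- With death ranked worst: 0.5(1 − *d*).

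| Excess early deaths | Shift in mean (days) | P(shorter), SAP rule | P(better), death worst |
|---|---|---|---|
| 1 | −0.05 | 0.504 | 0.495 |
| 2 | −0.11 | 0.509 | 0.491 |
| 5 | −0.27 | 0.52 | 0.48 |

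For five deaths: *d* = 5/110 = 0.0455, and 0.5 × 0.9545 + 0.0455 × 0.995 = 0.52, against 0.5 × 0.9545 = 0.48. The two rules fall on opposite sides of 0.5.

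**Timing of death.** The same model, with five excess deaths all on one day:

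| Day of death | Shift in mean (days) | P(shorter), SAP rule |
|---|---|---|
| 7 | 5 × (7 − 7.75)/110 = −0.03 | 0.50 |
| 10 | 5 × (10 − 7.75)/110 = +0.10 | 0.487 |
| 15 | 5 × (15 − 7.75)/110 = +0.33 | 0.479 |

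Only deaths earlier than a typical stay favour the arm. Later ones count against it.

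**Effect on the test.** This was simulated separately: unstratified Wilcoxon test, 4,000 runs, log-SD 0.5, deaths uniform on days 0.5 to 3.5. The chance of a nominally significant result in favour of the arm with more deaths is 2.2% with no excess, 4.1% with a 2% excess and 8.7% with a 5% excess. With death ranked worst the figures are 2.2%, 1.2% and 0.6%.

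**The case against.** Several objections have force.

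- **Status.** Length of stay is an additional variable in a Phase 2 study, tested without multiplicity control (SAP 10.0). The section has separate rehospitalisation and resource-use analyses, so length of stay does not carry the resource-use claim alone. This stands and limits the weight of the point.
- **Size.** One or two excess deaths move the mean by roughly a tenth to a fifth of its standard error, and five by about half. This stands.
- **Meaning.** As a count of bed-days used, ending the stay at death is literally correct. This also stands. The fault appears when a shorter stay is read as clinical benefit.
- **Death is visible elsewhere.** The win ratio ranks death first, deaths are listed under safety, and the DSMB reviews safety data at four points. A reader of the full report would see an excess of deaths. None of this changes the stand-alone length-of-stay estimates or p-values.

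A reader might also infer more than the documents support:

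- The EuroSCORE II exclusion above 7% might be taken as a plausible excess of about eight deaths in one arm. It is a limit on each participant's predicted risk and applies equally to all arms, so it says nothing about a difference between them.
- In-hospital deaths might be said to count as no rehospitalisation. SAP 10.3 states no such rule. Its 30-day window runs from discharge, and the section is silent on participants never discharged alive.
- The 60-day hospital days might be thought to carry the same bias into a test. They are only described.

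**Conclusion.** The point holds for the stand-alone hospital and ICU length-of-stay comparisons: an early in-hospital death is scored as a short, favourable stay. Bias arises only when early deaths differ between arms. Under the stated assumptions it is about 0.05 to 0.11 day for one or two excess deaths and 0.27 day for five. The rank comparison then falls on the wrong side of 0.5 relative to a ranking with death worst. The stay distribution, the number of deaths and their timing are all assumed. It would be wrong to say that in-hospital deaths in general are rewarded, because the advantage disappears for deaths at about the median stay and reverses after it.

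Two details of scope remain. Under SAP 6.1, a participant who dies before any ePatch ECG is outside the mITT population and drops out of these analyses altogether. The further version of hospital stay, counted from hospital admission, has no death rule of its own; if the same rule is applied, the same problem follows. The primary endpoint is unaffected. The change is worth making because it is cheap and removes a known direction of bias.

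**What to change.** In SAP 10.3:

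1. In the Van Elteren tests of hospital and ICU stay, give participants who die during that stay the worst rank. Make this the inferential comparison or, at the least, a prespecified sensitivity analysis beside the current rule.
2. Keep the ANOVA models and the death-truncated stay, labelled as a description of bed-days used, and report the number of in-hospital deaths by arm next to them.
3. State the death rule for the version of hospital stay that starts at hospital admission.
4. Optionally, describe days alive and out of hospital to Day 60 beside the 60-day hospital days.

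Restricting the ANOVA or the rehospitalisation comparison to participants discharged alive is not recommended, because it would condition a randomised comparison on survival after randomisation.

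The cost is SAP wording and minor programming; the dates and times of death and discharge are already used. The downside is that the rank test becomes a combined ranking of death and stay and no longer measures bed-days alone. The change should be made before the database lock for the interim/primary analysis, when SAP section 12.0 has the sponsor's study personnel unblinded.
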